9.0 Procedures Involved*

- 9.1 This study is a randomized control trial with stratification. Preliminary data from a preliminary FSDT will be used for exclusion, stratification, and randomization so that we can avoid any bias in results. The FSDT is scored on a 0–6-point scale with 0-1 categorically defined as good, 2-3 as moderate, and 4+ as poor. A participant will be excluded from the study if their score is defined as good or a 0-1 score. Then, stratification will be based upon the participant's categorical FSDT score of either moderate or poor to ensure equal representation of the category in each group. Participants will be randomly assigned to either the control group (hip activation HEP) or the experimental group (Hip activation plus movement retraining HEP). Individuals will receive their HEP protocol in an opaque envelope to ensure allocation concealment. The dependent variables are the FSDT score (statistical and clinical significance) and Gmed and Gmax sEMG activation (peak and mean).
- 9.2 Research procedures being performed and procedures being to monitor subjects for safety or minimize risks

Recruitment and Informed Consent Procedures

- Potential subjects will be recruited via word of mouth from people who are local to Shreveport, LA and local clinical/academic settings. Once they are recruited, meeting will be held for all potential participants to obtain informed consent. Then, the participant will complete a self-reported health questionnaire and a preliminary FSDT. If a potential participant cannot be

present at this meeting, a meeting will be scheduled with the investigators to obtain these measures.

- To ensure confidentiality, participants will be given a random identification number after their informed consent is obtained. Participant scores on the initial FSDT screening will be recorded by ID. Randomized stratification will take place following enrollment of all participants to ensure an equal distribution of FSDT scores between the control and experimental groups.
- Following enrollment, participants will sign up with their participant number for preliminary data collection in the motion analysis lab in room 2-217 in the SHPS at LSUHS. The participants will be instructed to wear shorts and advised to not wear leggings, tights, or pants or any lotions, both of which could impact EMG placement and data collection.

Anthropometric data collection procedures

- Age, sex, height, weight, BMI, and dominant lower extremity (LE) will be recorded in the rehabilitation faculty clinic by GD and DB during the first visit. The determinacy of the dominant leg is based on the leg chosen to kick a ball at a target.¹⁵

MVIC testing procedure:

- Participants will then take the elevator to the second floor and report to room 2-217 for sEMG and FSDT. Electrodes for sEMG will be placed on the gluteus maximus and gluteus medius muscles of the dominant leg via Seniam guidelines, and skin preparation following recommendations from The ABC's of EMG.¹⁶ The electrodes that will be used are self-adhesive Ag/AgCl Dual Electrodes by Noraxon. The placement of sEMG electrodes will be completed by GD for the female participants and DB for the male participants. Maximum Isometric Voluntary Contraction (MVIC) for the GMax and GMed muscle will be performed and recorded by GD and DB. SEMG data collection will be obtained for MVIC and during performance of the FSDT.
- The procedure for collection of the maximum volitional isometric contraction (MVIC) of the GMed will follow the protocol used in a study by Harput et al.¹⁷ The participant will lay on their side with their top leg extended at the knee and abducted and extended at the hip. The MVIC position of the GMax will follow the protocol used in a study by Selkowitz et al, with the knee flexed to 90 degrees in prone.^{18,19}

FSDT procedures

- Participants will be instructed on the procedure for the FSDT by MM. The FSDT consists of five consecutive repetitions of a forward step-down from a 20cm step, with one score given for the whole set of five repetitions.^{20,21} The participant will be allowed to take two practice repetitions before beginning the test. sEMG data and FSDT will be collected before and after the 8 week HEP.

HEP and Compliance Chart Education Procedures

- After the initial FSDT and randomization has been completed, the participant will be educated on the gluteal muscle activation exercises HEP by (GD or DB or MM) (control group) or movement retraining program and gluteal muscle activation exercise HEP by (GD or DB or MM) (experimental group). Participants will be educated the compliance chart by investigator (GD or DB or MM). Compliance chart data will be collected and analyzed during the third/final visits.
- All participants will receive the HEP for hip muscle activation training. The HEP for hip musculature activation consists of five isolated hip activation exercises including side-lying clams, side-lying clams with trunk activation via side-plank, side-lying hip abduction, side-lying hip abduction with trunk activation via side-plank, and fire hydrants all of which improve hip gluteal recruitment. See HEP for appropriate exercise positioning, dosage, frequency, and advised progressions.
- Only participants in the experimental group will receive the movement retraining program HEP. The HEP will be a combination of single leg RDL, single leg squat, and standing split squat that have been used in previous research and are proved to get significant Gmed activation.^{11,12,13} They will also participate in the gluteal activation HEP program that have been proved to increase hip musculature recruitment.
- A compliance chart will be given to the participants to track each time they perform the HEP. The participants in the control group and experimental group will take home their HEP, a compliance chart, then a yellow and red TheraBand. The participants will complete their HEP two days/week for eight weeks, with at least two rest days between sessions for muscle soreness prevention and document the completion of the session on the compliance chart.
- After the 4th week, both groups are to return to the clinic and asked to briefly perform exercises from their HEP so that their form can be reassessed with any modifications if needed along with any questions that they may have. Each participant following the 8-week period will be scheduled to return to the clinic to turn in their compliance form and perform follow-ups sEMG, weight, and FSDT using the same procedures as before.

Randomization of Group Allocation: Following the baseline EMG and FSDT measures, participants will be handed an opaque envelope containing their group allocation. Participants in the control group are indicated by a “0”, and intervention group by a “1”. A sequence of 1’s and 0’s will be generated by random generation in Excel, and the assignment will be made by sequential enrollment. To avoid unequal distribution of movement quality between groups, initial stratification in to “fair” and “poor” FSDT performance will be established after informed consent. Each strata will have an equal distribution of control and intervention envelopes.

9.3

Table of Events	# of times test or procedure will be performed
Written informed consent	1
Anthropometric assessment (height, weight, BMI, sex, age, leg dominance)	1
FSDT	3
sEMG	2
HEP Education	1
Compliance Chart Education	1
HEP Midpoint Check in	1
HEP	16
Compliance chart document	16

9.4 To reduce the risk of confidentiality, participants will be assigned identification numbers. All hardcopy data including group assignments will be stored in the PI's office in a locked drawer. All electronic data will be stored using OneDrive connected to school email addresses with a password. The investigator performing the data analysis will be blinded.

An informed consent document with participant identification numbers will be used to obtain consent from the participants. An identification number will be assigned to the name of each participant along with their group assignment. An identification number key will be used to maintain confidentiality when performing data collection and analysis, which will be stored on the PI's password protected computer. Only study members will have access to this document.

A sign-up sheet for the data collection days will be created that will allow participants to sign up with their assigned identification number. Investigators will use an excel sheet to collect data (see data collection form as part of submission). Participants will track their HEP performance on the compliance chart that will be provided to each participant. A paper copy of the HEP with pictures, written instructions, and a QR code for video instructions will be given to the participants.

To reduce the risk of muscle soreness, participants will be educated on appropriate exercise performance and to space the sessions at least two days apart. Once all hip activation exercises can be completed for one minute on the dominant LE without a break, participants will be educated to add the yellow TheraBand. Once the exercises can be completed for one minute with the yellow TheraBand on the dominant LE without a break, participants will be educated on progressing to the red TheraBand that has a higher resistance.

To reduce the privacy risk of participants being recorded on video for data collection and the possibility of the video recording being lost or exposed, all electronic data will be stored using Sharepoint connected to school email

addresses with a password. This information will also be kept private by utilizing the assigned participant identification numbers.

Another possible risk of being in this study is a modesty risk that includes the exposure of a participant's buttocks when doing sEMG electrode placement for data analysis. To reduce this modesty risk, an investigator of the same sex will be doing the electrode placement.

One risk associated with sEMG electrode placement includes potential skin irritation and a rash occurring from wearing or removing the sEMG electrode patches that stick to your skin due to the gel that is used with them. Also, the skin will be wiped with an alcohol pad which could cause possible irritation as well. If there is hair on the participant's buttocks, irritation or discomfort could occur when the electrode patch is removed. To reduce this physical risk, the investigator doing the sEMG electrode placement and removal will be careful to avoid causing excessive irritation to the skin area and will explain the risks to the participant.

Upon the first session, the data collection will include participant age, height, weight, BMI, dominant LE, in addition to the following pre- and post- intervention: FSDT, sEMG from gluteus medius and maximus, recorded FSDT video. Compliance chart data will be collected post-intervention.

Will any data be shared with the drug/device manufacturer?

N/A

- Will you collect any data for patients outside Ochsner Shreveport and Monroe (i.e. from sites like New Orleans, Baton Rouge, Lafayette etc.) from the databases stated in the protocol?

Yes No

- Please confirm if any data will be transferred to the sites outside Ochsner Shreveport & Monroe.

Yes No

- If yes, please list the data that will be transferred and how.

9.5 N/A

10.0 Data and Specimen Banking

10.1 N/A

10.2 N/A

10.3 N/A

11.0 Data Management and Confidentiality

11.1 Data analysis plan and statistical procedures.

FSDT

Data processing: Each participant will perform a pre- and post- intervention trial for the FSDT that will be scored. The FSDT consists of 5 repetitions of a step-down task. One score is given for the whole test. One raters will score the FSDT (MM).

Data analysis: For the FSDT data, a 2x2 repeated measures ANOVA will be performed with significance set at alpha = .05. Post hoc testing will be used if significant differences are detected with the ANOVA. Tukey's HSD test will be used as the post hoc test, with significance set at alpha = .05.

sEMG

Data processing: Raw sEMG signals will be bandpass filtered between 10-500 Hz. The signal will be rectified, then smoothed using the Root Mean Square method with a 50ms window. The signal from the FSDT and UPST will be normalized to the MVIC obtained during the MVIC testing.

Data analysis: Following MVIC normalization, sEMG activity will be recorded during each of the outcome measures. Each FSDT step-down repetition will be analyzed as a separate trial, and the mean and peak activation for GMax and GMed will be extracted from each of the 5 trials. A mean value for each variable (mean and peak activation of GMax, mean and peak activation of GMed) will be calculated and recorded at the pre-and post-test sessions.

For the sEMG data, a 2x2 repeated measures ANOVA will be performed for each measurement (mean, peak) for each muscle (Gmed, Gmax), with significance set at alpha = .05. Post hoc testing will be used if significant differences are detected with the ANOVA. Tukey's HSD test will be used as the post hoc test, with significance set at alpha = .05.

11.2 G* power (Heinrich-Heine-University Dusseldorf, Dusseldorf, Germany) software was used to perform a priori power analysis to determine the

required N for this investigation. Data from [name] Et Al. (2025) study reported a Cohen's d of 0.58 (d=0.58).⁵ An N of 26 was calculated to achieve significant results with beta= .80 and alpha =.05 for a two-tailed hypothesis from an interaction effect of the 2x2 repeated measures ANOVA. Assuming 20% attrition, plus an additional 10% for FSDT screening failures, a final N=38 is required for this study.

- 11.3 To reduce the risk of loss of confidentiality, participants will be assigned ID numbers on their informed consent form. All hardcopy data will be stored in a locked drawer in room 2-236 in the SHPS at LSUHS. All electronic data will be stored using Sharepoint/OneDrive connected to school email addresses with a password. The investigator performing the data analysis will be blinded. Participants will be identified by their ID number throughout the study, and group assignment will be recorded by ID number. A sign-up sheet for data collection times will also use ID number. Throughout the study, data will be recorded by ID number on the data collection sheet attached to this submission. For the participants to track their home exercise sessions, a compliance chart will be created for them again with only ID number attached to the compliance chart.

- 11.4 The student investigators (DB, GD, MM) will be educated on the proper procedures of the FSDT, sEMG data collection, and the HEP by the primary investigator (EM) and co-investigator (DF). The FSDT will be analyzed by the three student investigators (DB, GD, MM). The student investigators (DB, GD, MM) will record and average their scores for the FSDT following the completion of five repetitions to improve the quality of the data. (Super script). The sEMG electrodes will be placed on the female participants by GD. MM will explain the FSDT procedure to every participant. DB, GD, MM will explain the hipactivation exercises on the HEP and will explain the movement retraining program HEP and the QR code access for videos. DB, GD, and MM will explain the compliance chart to the participants. The primary investigator (EM) is a board-certified orthopedic physical therapist with 8 years of experience, who has published research on this test. (super script) The co-investigator? (DF) is also a board-certified orthopedic physical therapist with 13 years of experience, who also has published research on this test with the primary investigator.

- 11.5 The data that will be collected during the study includesheight, weight, BMI, sex, leg dominance, MVIC of each muscle group, FSDT pre and post HEP, recorded FSDT video, sEMG from gluteus medius and maximus on the dominant leg during FSDT pre and post HEP, and HEP compliance. Data storage will follow the guidelines in section 9.4. The data will be stored for the duration of the study and throughout the following semester while analyzing and finalizing data for presentation. The data will only be

kept up to one year after the completion of the data analysis in the event that the research wants to be continued. The only people who will have access to this information will be the primary investigator and student investigators (EM, DB, GD, MM) since the co-investigator (DF) that is doing the data analysis will be blinded. The primary investigator and student investigators are responsible for the receipt and transmission of the data. The student investigators (DB, GM, MM) are responsible for data processing. Data will be manually transported to EM office room 2-236 in the SAHP at LSUHS. Electronic data will remain on Sharepoint.

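### Sections 11.1 and 11.4 disagree on whether one student or three score the FSDT, and under either version the raters also teach both arms and are not masked to group

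*Combined protocol and SAP*

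**What the plan says.** **Who scores.** Section 11.1, under FSDT data processing, reads "One raters will score the FSDT (MM"), and says one score is given for the whole test. Section 11.4 reads "The student investigators (DB, GD, MM) will record and average their scores for the FSDT following the completion of five repetitions".

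**Who teaches.** Section 11.4 also says "DB, GD, MM will explain the hipactivation exercises on the HEP and will explain the movement retraining program HEP". Section 9.2 names the same three students as alternatives for the control program and again for the experimental one: "movement retraining program and gluteal muscle activation exercise HEP by (GD or DB or MM) (experimental group").

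**When group becomes known.** Section 9.2: "Following the baseline EMG and FSDT measures, participants will be handed an opaque envelope containing their group allocation". The mid-study check is described as "After the 4th week, both groups are to return to the clinic and asked to briefly perform exercises from their HEP", with no staff named.

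**Who is blinded.** Sections 9.4 and 11.3 blind the person who analyses the data. Section 11.5 identifies that person as the co-investigator and gives data access to the principal investigator and the students. Section 19.1 provides a separate room for teaching and gives the analyst's blinding as the reason. Section 24.2 has the co-investigator leave during teaching, and 24.3 withholds exercise-program information from the co-investigator alone. Section 24.1 uses the term single-blind without saying who is blind. The key linking ID to group is on the principal investigator's "password protected computer. Only study members will have access to this document" (9.4).

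**The concern.** There are two linked problems.

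First, the scoring rule for the main outcome is contradictory. One rater and the mean of three raters are different measurements, with different possible values, and the good, moderate and poor categories in 2.2 are defined only for whole numbers.

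Second, the FSDT depends on an observer's judgement, and the observers are the people listed to deliver the interventions. A rater who taught a participant knows that participant's arm at the week-8 test. Blinding the analyst cannot remove a lean already present in the recorded scores. An arm difference in score (SA1) or category (SA2) would then be open to rater expectation as an explanation. SA5 also uses FSDT change. The sEMG aims (SA3, SA4) are not directly affected.

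**Working it through.** **The texts side by side**

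| Question | Section 11.1 version | Section 11.4 version |
|---|---|---|
| Raters | 1 student | 3 students, averaged |
| Are raters listed to teach both arms (9.2, 11.4)? | Yes | Yes, all three |
| Does a rater know the participant's arm at week 8? | Possible; 9.2 lists the teachers with *or* | Yes; whoever taught is among the raters |
| Is the rater named in any blinding measure? | No | No |

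Other routes to unmasking: the 9.4 key is open to study members with no exception for the rater; the week-4 check names no staff; and 24.2 allows teaching in the data-collection room behind a divider, which blocks sight but not sound. Section 19.1 specifies a separate room, so 24.2 and 19.1 also need to be aligned.

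**Effect on the scale.** The mean of three whole-number scores from 0 to 6 has 19 possible values. Those strictly between 1 and 2 are 4/3 = 1.33 and 5/3 = 1.67. Those strictly between 3 and 4 are 10/3 = 3.33 and 11/3 = 3.67. None of the four belongs to a category in 2.2. SA2 is affected, and so are eligibility and strata if screening is scored the same way.

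**The plan's own sample size.** This is not in dispute; it supplies the numbers per arm. With f = 0.58/2 = 0.29, two groups, two times and an assumed pre-post correlation of 0.5, the noncentrality is 26 × 0.29² × 2/(1 − 0.5) = 8.75 and power is 0.81, so N = 26 reproduces. Inflation: 26/0.70 = 37.1, which reaches 38 when rounded up to an even number.

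**Illustration of a lean.** The 2×2 interaction is equivalent to a two-sample t-test on change scores. Assumptions, none of them in the documents: no true effect; normal change scores; SD of change 1.0 to 1.5; and the teaching student scores experimental participants one point too favourably and controls correctly. The test is two-sided at 5%.

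Numbers per arm: 26/2 = 13; and 38 × 0.8/2 = 15.2, taken as 15, if all 38 are randomised. If the 10% screening loss also comes out of the 38, 38 × 0.9 × 0.8/2 = 13.7.

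*Section 11.4 version.* One of three averaged raters leans, so each experimental score moves 1/3 point. Noncentrality = (0.333/SD) × √(n/2).
- n = 13: 0.850 at SD 1.0 gives 12.9%; 0.567 at SD 1.5 gives 8.5%.
- n = 15: 0.913 at SD 1.0 gives 14.3%; 0.609 at SD 1.5 gives 9.0%.

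*Section 11.1 version.* The sole rater taught about a third of the experimental arm (even split assumed), and those participants move one full point. By simulation with 200,000 runs:
- 4 of 13 shifted: 9.7% at SD 1.0; 7.3% at SD 1.5.
- 5 of 15 shifted: 11.8% at SD 1.0; 8.2% at SD 1.5.
- None shifted: 5.0%, as it should be.

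**The case against.** The best reply is that the contradiction is only a drafting slip and that the masking problem depends on which section governs. If 11.1 governs, the sole rater might teach few participants or none, because 9.2 lists the three students as alternatives. Certain exposure arises only under 11.4, which carries visible drafting remnants. Roles are still to be assigned in a delegation document (section 20) that is not in the file. No text says the shared master data sheet holds group or exercise-program fields. The lean and the SDs are invented, and one SD is used for single and averaged scores although averaging would reduce rater noise. Averaging was also adopted to improve data quality.

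Much of this is fair on degree. Exposure under 11.1 is a risk rather than a certainty; the content of the master sheet is an inference; and the figures are illustrations only. None of it removes the core. No text seen separates scoring from teaching or masks the rater, and a later delegation document cannot by itself resolve two protocol sections that conflict. Averaging reduces random rater error, but it does not mask the raters, and it creates scores with no category.

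**Conclusion.** The concern holds and should be fixed before enrolment. The contradiction between 11.1 and 11.4 is wrong as written. The absence of rater masking follows from the text under either version, and it can be repaired cheaply. Because allocation follows the baseline FSDT, a lean would fall on the week-8 score and pass directly into the planned interaction test.

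The size of any bias is unknown. Under the stated assumptions the false-positive rate is about 8-13% (13 per arm) or 9-14% (15 per arm) on the 11.4 version, and about 7-10% or 8-12% on the 11.1 version, against a nominal 5%. The severity rests on the wording of the plan and not on these figures. The sample size is not affected.

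**What to change.** First make 11.1 and 11.4 agree on who scores. Then choose one of two routes.

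**(a) A sole masked rater.** Name one student who does no exercise or compliance-chart teaching, envelope hand-out, week-4 check or compliance collection. That student has no access to the group key or to any group or exercise-program fields on shared files. The student named in 11.1 fits, since 9.2 gives electrode work to the other two: "The placement of sEMG electrodes will be completed by GD for the female participants and DB for the male participants". Amend 9.2, 9.4, 11.4 and 11.5. Amend 24.2 so that teaching and the week-4 check always take place in the separate room of 19.1, and 24.3 so that exercise-program information is withheld from the rater too. Ask the teaching students not to mention group in the rater's presence. Cost: wording and task reassignment; two students instead of three share the teaching; averaging is given up; teaching can no longer share the data-collection room.

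**(b) Masked video scoring.** Amend 11.5 so that the blinded co-investigator scores the recorded baseline and week-8 videos, coded and shuffled with arm and visit hidden, as the score of record. Bar the co-investigator from the key in 9.4. Lock the scores before passing on any file with a group column, because 9.2 states what codes 0 and 1 mean. Live scores still decide eligibility and strata, so state a whole-number rule for them. Cost: up to 38 × 2 = 76 videos, at an assumed 3 to 5 minutes each, which is 3.8 to 6.3 hours plus coding; possibly less detail than live viewing; rater and analyst become the same person.

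Under both, ask participants not to mention their exercises at post-test, and collect the compliance form away from the rater. If averaging is kept anywhere, state how averages map to the categories. Neither route needs new staff or extra participant visits.

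### The 2x2 repeated measures ANOVA adjusts for neither the baseline value nor the randomisation stratum, which gives up precision that a trial with 26 completers needs

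*Combined protocol and SAP*

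**What the plan says.** Section 9.1 stratifies randomisation on the "categorical FSDT score of either moderate or poor to ensure equal representation of the category in each group", and section 9.2 gives each stratum equal numbers of control and intervention envelopes. FSDT and sEMG are recorded before and after the 8-week programme (section 9.2).

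For the FSDT score, section 11.1 states: "For the FSDT data, a 2x2 repeated measures ANOVA will be performed with significance set at alpha = .05". For sEMG it applies the same model "for each measurement (mean, peak) for each muscle (Gmed, Gmax), with significance set at alpha = .05". Tukey's HSD follows a significant result. No section names a covariate, a stratum term or an ANCOVA. The baseline value enters only as the first level of the time factor.

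Section 11.2 bases the sample size on the same test: "An N of 26 was calculated to achieve significant results with beta= .80 and alpha =.05 for a two-tailed hypothesis", derived "from an interaction effect of the 2x2 repeated measures ANOVA".

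**The concern.** The interaction in a two-arm, two-visit ANOVA compares mean change between arms. That subtracts the whole baseline value, as if a participant one point worse at baseline were expected to be one point worse at week 8. With measurement error in a 0-6 score, and with entry restricted to scores of 2 or more, some regression to the mean is expected, so the true slope is probably below 1. Subtracting too much adds noise. ANCOVA estimates the slope instead. Under randomisation it targets the same arm difference, and in large samples it is never less precise. It also corrects for chance baseline imbalance, which is a real risk with about 13 completers per arm.

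The stratum is a separate omission: a factor that constrained the allocation is missing from the model.

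At stake are the width of the confidence intervals and the power for FSDT and four sEMG outcomes, in a trial with little to spare.

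**Working it through.** **Inputs.** From section 11.2: d = 0.58, two-sided alpha 0.05, power 0.80 (written there as beta), N = 26 evaluable and 38 in total. The pre-post correlation r is not given, so it is an assumption and is shown as a range.

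**1. The plan's own figure.** For a group-by-time interaction with f = 0.58/2 = 0.29, m = 2 visits and r = 0.5:

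lambda = f² × N × m / (1 − r) = 0.0841 × 26 × 2 / 0.5 = 8.746, on 1 and 24 df. Power is 0.810.

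So N = 26 reproduces at r = 0.5. With the same f, r = 0.3 would need 36 and r = 0.7 would need 18. The total follows as 26/0.70 = 37.1, rounded up to 38.

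**2. The difference this implies.** As a change-score test, lambda = delta² × N / [4 × 2(1 − r)]. At r = 0.5 that is delta² × 6.5 = 8.746, so delta = 1.16 SD between arms. If 0.58 SD were the between-arm difference, the change-score test would need N = 96 for 80% power.

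**3. Variance of the two analyses.** With equal pre and post SDs, in units of SD²:

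- change score: 2(1 − r)
- ANCOVA on baseline: 1 − r²
- ratio: (1 − r²) / [2(1 − r)] = (1 + r)/2

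At r = 0.5 the ratio is 0.75, so 26 completers carry the information of 26/0.75 = 34.7, about 35.

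**4. Power at N = 26.** For ANCOVA, lambda = delta² × N / [4(1 − r²)] on 23 df. At r = 0.5 and delta = 1.16 that is 34.99/3 = 11.66.

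| r (assumed) | Variance ratio | 1.16 SD: change → ANCOVA | 0.58 SD: change → ANCOVA |
|---|---|---|---|
| 0.3 | 0.65 | 0.67 → 0.84 | 0.22 → 0.32 |
| 0.5 | 0.75 | 0.81 → 0.905 | 0.295 → 0.37 |
| 0.7 | 0.85 | 0.96 → 0.98 | 0.45 → 0.51 |
| 0.8 | 0.90 | 0.994 → 0.997 | 0.61 → 0.66 |

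At r = 0.5 and 1.16 SD, the N for 80% power falls from 26 to 20.

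**5. Effect of the stratified allocation** (simulation, N = 26, r = 0.5, normal scores, delta 1.16 SD).

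- *Stratum from a separate screening test.* The variance ratio for baseline plus stratum is about 0.73. Power rises from 0.81 to about 0.90, and type I error stays near 5%.
- *Stratum from a median split of the same baseline score.* Power is 0.87 for change, 0.90 for ANCOVA on baseline, and 0.89 with the stratum added.

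The documents support the first case. The table in section 9.3 lists three FSDTs, and section 9.2 puts a screening FSDT at the consent meeting and a further FSDT in the laboratory before the envelope is opened.

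**6. Bounded integer scores.** A simulation with 0-6 integer scores, entry at 2 or more and stratified allocation gave 10-22% lower variance for baseline plus stratum. For a true 1-point effect, power of 0.50-0.65 rose to 0.60-0.70, with type I error of about 5%. These ranges depend on the score distributions assumed.

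**The case against.** The strongest reply is that nothing planned is invalid. Under randomisation the change-score comparison is unbiased, leaving out a stratification factor tends to make the test conservative, and the analysis matches the sample-size calculation. Baseline is not discarded either, since it enters through the change. All of this is right. The loss is therefore the gap between a change score and ANCOVA, not between ignoring baseline and using it.

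The size is also open to challenge, and these qualifications stand:

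- The ratio (1 + r)/2 needs equal SDs. If the post SD were 1.25 times the pre SD (an assumption), the ratio would be 1.5625(1 − r²) / (2.5625 − 2.5r), which is 0.89 at r = 0.5 and 0.98 at r = 0.7. The documents give neither the SDs nor r.
- If the stratum were a split of the same baseline score, stratification would already recover much of the gain for FSDT. The variance reduction for the full model could then be only 7-8%. The design described points to a separate screening test, and the sEMG outcomes are not stratified on in either case.
- The stratum adds little precision once the baseline value is in the model. The main reason to include it is to match the randomisation.
- Adherence, the exposure for the dose-response aim, has no baseline value, so the point covers the FSDT score and the sEMG variables only.

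None of these gives a reason to prefer the change-score test as the primary analysis.

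**Conclusion.** The concern holds. The plan collects a baseline value for the FSDT score and for each sEMG variable, and it randomises within FSDT strata, yet it adjusts for neither. This is avoidable inefficiency, not bias.

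At the correlation that reproduces the plan's own N, the loss is about a quarter of the variance, or roughly 9 points of power at the implied difference. Allowing for integer scores, a 10-22% reduction in variance is a fair expectation for FSDT. The benefit shrinks towards nothing as r approaches 1 or if the week-8 SD is clearly larger than the baseline SD. Adjustment does not rescue the trial if the true difference is 0.58 SD: at r = 0.5, power would still be only 0.37.

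**What to change.** In section 11.1, replace the primary analysis with a linear model for each outcome: week-8 value on arm, the baseline (laboratory-visit) value of the same outcome, and screening stratum (moderate or poor). Report the adjusted arm difference with its 95% CI, with participants analysed in the arm assigned. Apply it to the FSDT score and to mean and peak activation of each muscle. State that the stratum comes from the screening FSDT and the covariate from the laboratory FSDT. The 2x2 ANOVA can stay as a sensitivity analysis.

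The cost is wording only, with no new data or visits. Two extra parameters move the residual df from 24 to 22 and the critical t from 2.064 to 2.074. Estimating them costs a little more variance, which the simulations in the working already include. Make the change before outcome data are seen, because covariates added afterwards would look selective.
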